3.2 Post Study Access to Therapy

At the end of the study, the sponsor will not continue to supply study drug to subjects/investigators unless the sponsor chooses to extend the study. The investigator should ensure that the subject receives appropriate standard of care to treat the condition under study.

3.3 Study Population

For entry into the study, the following criteria MUST be met.

3.3.1 Inclusion Criteria

1) Signed Written Informed Consent

a) Subjects must be willing and able to give signed and dated written informed consent.

2) Target Population

- a) Subject must have type 1 diabetes with inadequate glycemic control, defined as central laboratory $A1C \ge 7.0\%$ and $\le 10.0\%$, obtained at the screening visit (Note: A one-time central laboratory re-test of the A1C is allowed in subjects with an initial central laboratory A1C of 6.8% or 10.2% who are otherwise eligible, as determined by the Investigator.)
- b) Insulin use, either multiple doses (at least 2x/day) of insulin consisting of long-acting (glargine or detemir) plus short-acting prandial insulin or on insulin pump (continuous subcutaneous insulin infusion, CSII), for at least 12 months and initiation of insulin immediately after diagnosis of diabetes. [Method of insulin administration (multiple daily injections or CSII) must have been stable for at least 3 months prior to Day -3. In addition, the dose of basal insulin must have remained stable (within 20% variance of the total daily dose) for the 2 weeks preceding Day -3 (per subject report)]
- c) Central laboratory C-peptide value of < 0.7 ng/mL at screening
- d) BMI 18.5 to 35.0 kg/m², inclusive at screening.

3) Age and Reproductive Status

- a) Men and women, ages 18 to 65 years old.
- b) Women of childbearing potential (WOCBP) and men must be using an acceptable method of contraception to avoid pregnancy throughout the study in such a

manner that the risk of pregnancy is minimized. See Section 3.3.3 for the definition of WOCBP.

- c) WOCBP must have a negative serum or urine pregnancy test (minimum sensitivity 25 IU/L or equivalent units of HCG) within 24 hours prior to the start of investigational product.
- d) Women must not be breastfeeding

3.3.2 Exclusion Criteria

1) Target Disease Exclusions

- a) History of T2DM, maturity onset diabetes of young (MODY), pancreatic surgery or chronic pancreatitis.
- b) Any use of oral hypoglycemic agents within 12 months prior to the Day -3 visit.
- c) History of diabetes ketoacidosis (DKA) within 24 weeks prior to the Day -3 visit.
- d) History of diabetes insipidus.
- e) History of hospital admission for glycemic control (either hyperglycemia or hypoglycemia) within 6 months prior to the Day -3 visit
- f) Frequent episodes of hypoglycemia as defined by more than one episode requiring assistance, emergency care (paramedics or emergency room care) or glucagon therapy, or more than 2 unexplained episodes of symptomatic hypoglycemia within 3 months prior to Day -3. An unexplained event is defined as an event that cannot be explained by circumstances such as dietary (e.g. missed meal), strenuous exercise, error in insulin dosing, etc.
- g) Hypoglycemic unawareness.
- h) History of Addison's disease or chronic adrenal insufficiency.

2) Medical History and Concurrent Diseases

Any of the following CV/Vascular Diseases within 6 months of the screening visit:

- a) Myocardial infarction
- b) Cardiac surgery or revascularization (coronary artery bypass surgery [CABG]/percutaneous transluminal coronary angioplasty [PTCA])
- c) Unstable angina
- d) Unstable congestive heart failure (CHF)

- e) CHF New York Heart Association (NYHA) Class III or IV (see Appendix 1)
- f) Transient ischemic attack (TIA) or significant cerebrovascular disease
- g) Unstable or previously undiagnosed arrhythmia

3) Physical and Laboratory Test Findings

- a) Aspartate aminotransferase (AST) > 2X Upper limit of normal (ULN)
- b) Alanine aminotransferase (ALT) > 2X ULN
- c) Serum total bilirubin > 2X ULN
- d) Estimated GFR (eGFR) by the Modification of Diet in Renal Disease (MDRD) formula ≤ 60 mL/min/1.73m2. The renal function, eGFR will be estimated by the abbreviated MDRD, using laboratory measurements of serum creatinine collected at screening [eGFR (mL/min/1.73m2) = 175 x (standardized Scr)-1.154 x (Age)-0.203 x (0.742 if female) x (1.212 if Black)].
- e) Hemoglobin ≤ 11.0 g/dL (110 g/L) for men; hemoglobin ≤ 10.0 g/dL (100 g/L) for women.
- f) Creatine kinase (CK) > 3X ULN
- g) Positive for hepatitis B surface antigen or anti-hepatitis C virus antibody.
- h) Abnormal Free T4

Note: abnormal TSH value at screening will be further evaluated for free T4.Subjects with abnormal free T4 values will be excluded. A one-time retest may be allowed, as determined by the Investigator, after a minimum of 6 weeks following the adjustment of thyroid hormone replacement therapy in subject who have had a prior diagnosis of a thyroid disorder and who are currently receiving thyroid replacement therapy. Such cases should be discussed with the Sponsor prior to re-testing. The subject must have all screening procedures and laboratory assessments performed as part of this re-test, and all of these must meet enrollment eligibility criteria. The subject's number will, however, remain the same as initially assigned.

4) Allergies and Adverse Drug Reaction

a) Allergies or contraindication to the contents of dapagliflozin tablets or insulin.

5) Renal, Hepatic, Hemotological/Oncological Diseases/Conditions

- a) History of unstable or rapidly progressing renal disease.
- b) Conditions of congenital renal glucosuria
- c) Renal allograft

dapagliflozin	MB102072
BMS-512148	Clinical Protocol

- d) Significant hepatic disease, including but not limited to, chronic active hepatitis and/or severe hepatic insufficiency.
- e) Documented history of hepatotoxicity with any medication
- f) Documented history of severe hepatobiliary disease
- g) History of hemoglobinopathy, with the exception of sickle cell trait (SA) or thalassemia minor; or chronic or recurrent hemolysis.
- h) Donation of blood or blood products to a blood bank, blood transfusion, or participation in a clinical study requiring withdrawal of > 400 mL of blood during the 6 weeks prior to the enrollment visit.
- i) Known immunocompromised status, including but not limited to, individuals who have undergone organ transplantation or who are positive for the human immunodeficiency virus.
- j) Malignancy within 5 years of the screening visit (with the exception of treated basal cell or treated squamous cell carcinoma of the skin)

6) Other Exclusion Criteria

- a) Prisoners or subjects who are involuntarily incarcerated
- b) Subjects who are compulsorily detained for treatment of either a psychiatric or physical (eg, infectious disease) illness
- c) Replacement or chronic systemic corticosteroid therapy, defined as any dose of systemic corticosteroid taken for > 4 weeks within 3 months prior to Day -3 visit.

NOTE: Topical or inhaled corticosteroids are allowed.

- d) Any unstable endocrine, psychiatric, rheumatic disorders as judged by the Investigator.
- e) Subject is, in the judgment of the Investigator, unlikely to comply with the protocol or has any severe concurrent medical or psychological condition that may affect the interpretation of efficacy or safety data.
- f) Subject with any condition which, in the judgment of the Investigator, may render the subject unable to complete the study or which may pose a significant risk to the subject.
- g) Subject is currently abusing alcohol or other drugs or has done so within the last 6 months.
- h) Subject is a participating investigator, study coordinator, employee of an investigator or immediate family member of any of the aforementioned.

dapagliflozin	MB102072
BMS-512148	Clinical Protocol

- i) Previous participation in a clinical trial with dapagliflozin (BMS-512148) and/or with any other SGLT2 inhibitors.
- j) Administration of any other investigational drug within 30 days of planned enrollment to this study.
- k) No clinical conditions or clinically significant abnormalities, in any laboratory value(s) collected after screening and prior to randomization which, in the Investigator's judgment, should preclude entry into the treatment period

Eligibility criteria for this study have been carefully considered to ensure the safety of the study subjects and to ensure that the results of the study can be used. It is imperative that subjects fully meet all eligibility criteria.

3.3.3 Women of Childbearing Potential

Women of childbearing potential include any female who has experienced menarche and who has not undergone successful surgical sterilization (hysterectomy, bilateral tubal ligation, or bilateral oophorectomy) or is not postmenopausal. Post menopause is defined as:

- Amenorrhea \geq 12 consecutive months without another cause and a documented serum follicle stimulating hormone (FSH) level >35 mIU/mL or
- Women with irregular menstrual periods and a documented serum follicle stimulating hormone (FSH) level > 35 mIU/mL or
- NOTE: FSH level testing is not required for women ≥ 62 years old with amenorrhea of ≥ 1 year
- Women on hormone replacement therapy (HRT)

Women who are using oral contraceptives, other hormonal contraceptives (vaginal products, skin patches, or implanted or injectable products), or mechanical products such as an intrauterine device or barrier methods (diaphragm, condoms, spermicides) to prevent pregnancy, or are practicing abstinence or where their partner is sterile (eg, vasectomy) should be considered to be of childbearing potential.

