3 INVESTIGATIONAL PLAN

3.1 Study Design and Duration

The MB102072 is a randomized, double-blind, 5-arm, parallel-group, placebo-controlled exploratory Phase 2a pilot study to evaluate the safety, tolerability, PK and PD of dapagliflozin in subjects with type 1 diabetes who have inadequate glycemic control despite insulin use. Approximately 70 subjects on insulin monotherapy with central laboratory enrollment A1C \geq 7.0% and \leq 10.0% will be eligible for randomization in a 1:1:1:1:1 ratio into one of the following five blinded treatment arms:

- Dapagliflozin 1 mg QD
- Dapagliflozin 2.5 mg QD
- Dapagliflozin 5 mg QD
- Dapagliflozin 10 mg QD
- Matching placebo

Subjects will receive dapagliflozin or matching placebo for a total of 14 days and will be in-patient from Day -3 to Day 7. Randomization will be stratified by body mass index (BMI) categorization ($\leq 23 \text{ kg/m}^2 \text{ vs.} > 23 \text{ kg/m}^2$) and method of insulin administration (pump or daily injections) to ensure equal representation across all treatment groups. Subjects will receive standardized diets and provided guidance for adjustment of insulin dosing during the inpatient stay. Subjects will be monitored closely with regard to safety parameters, including vital signs, safety laboratory tests and adverse events.

dapagliflozin	MB102072
BMS-512148	Clinical Protocol

In addition to the routine safety laboratory tests, the following parameters will be closely monitored:

- Urinary ketones by urine dipstick, daily
- Fluid intake and output, daily (during inpatient portion of the study only)
- Serum β -hydroxybutyrate at baseline Day -2, Day 1, day 7, Day 14 and Day 21
- Body weight at screening, daily during inpatient portion of the study (starting day -2) and at each outpatient visit

* Subjects will be inpatient from Day -3 to Day 7 and then have outpatient visits on Day 10 (± 1 day), Day 14 and a discharge visit on Day 21 (± 2 days).

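### Minor: section 3.3.3 counts a woman with irregular periods as postmenopausal on a documented FSH above 35 mIU/mL, so she can fall outside the contraception and pregnancy-testing rules

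*Protocol*

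**What the plan says.** Protocol section 3.3.3 defines a woman of childbearing potential (WOCBP) as one past menarche who has not been surgically sterilised "or is not postmenopausal". It then lists what counts as post menopause:

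- First bullet: amenorrhea of at least "12 consecutive months without another cause and a documented serum follicle stimulating hormone (FSH) level >35 mIU/mL".
- Second bullet, joined by 'or': "Women with irregular menstrual periods and a documented serum follicle stimulating hormone (FSH) level > 35 mIU/mL".
- A note: "FSH level testing is not required for women ≥ 62 years old with amenorrhea of ≥ 1 year".
- A final bare bullet naming HRT users.

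The closing paragraph returns some women to WOCBP status. It covers users of hormonal, intrauterine or barrier contraception, and women who are abstinent or have a sterile partner ("or are practicing abstinence or where their partner is sterile (eg, vasectomy) should be considered to be of childbearing potential").

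Several rules depend on that status. Inclusion criterion 3b in section 3.3.1 begins "Women of childbearing potential (WOCBP) and men must be using an acceptable method of contraception" and refers to 3.3.3 for the definition. Criterion 3c asks WOCBP for a negative pregnancy test within 24 hours before the first dose. Section 3.4.3 tells WOCBP to contact the investigator if they suspect pregnancy. The urine pregnancy row of Table 5.1.1 and the HCG entry in Appendix 2A are also restricted to WOCBP.

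**The concern.** The second bullet drops the condition that its neighbours keep. On its wording, a woman with irregular periods is still menstruating, yet a single documented FSH value moves her out of the WOCBP group. The value needs no date and no repeat. Eligible ages run from 18 to 65, so perimenopausal women can enrol.

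The closing paragraph brings back women using contraception, abstinent women and women with a sterile partner. It does not bring back a woman who uses no method, is not abstinent and has a fertile partner, although she is the one most exposed to pregnancy. At stake is a pregnancy that is dosed without having been tested for. The protocol treats pregnancy seriously elsewhere: section 3.5 makes it a reason for mandatory discontinuation, and sections 6.1.1 and 6.4 require reporting within 24 hours. Those rules work only once the pregnancy is known.

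**Working it through.** There is no plan figure to reproduce. The check compares the rules, settles the reading of the stem and counts the tests and doses.

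**1. The three postmenopause rules (section 3.3.3)**

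| Rule | Amenorrhea required | FSH > 35 required |
|---|---|---|
| First bullet | at least 12 months, no other cause | yes |
| Age 62 or over note | at least 1 year | no |
| Irregular-periods bullet | none | yes |

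Only the third rule has no amenorrhea condition.

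**2. The stem.** It joins 'not sterilised' and 'not postmenopausal' with 'or'. Applying both possible readings:

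| Woman | WOCBP under literal 'or' | WOCBP under 'and' |
|---|---|---|
| Unsterilised, irregular periods, FSH > 35 | yes | no |
| Sterilised, premenopausal | yes | no |
| Unsterilised, premenopausal | yes | yes |

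The literal reading makes a sterilised premenopausal woman WOCBP and leaves the postmenopause list almost without effect. The evident meaning is 'and', and under it the woman in the first row is not WOCBP.

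**3. Tests missed (Table 5.1.1).** The urine pregnancy row is marked at screening, Day -2, Day -1, Day 10, Day 14/ET and Day 21. That is 3 before dosing + 3 after = 6. The Day -1 test can serve for criterion 3c, so there is no seventh.

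**4. Doses at risk.** Section 3.1 has subjects on treatment "for a total of 14 days and will be in-patient from Day -3 to Day 7". Inpatient doses, Days 1 to 7: 7. Outpatient doses, Days 8 to 14: 7. A pregnancy present at entry could meet up to 7 + 7 = 14 doses; one conceived in the outpatient dosing week could meet at most 7.

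**5. Women affected.** The protocol gives no number. Assuming 0 to 2 women of 70: 0/70 = 0% to 2/70 = 2.9%. Tests missed: 0 × 6 = 0 to 2 × 6 = 12, of which at most 2 × 3 = 6 are before dosing.

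**The case against.** - **The bullets are alternatives.** Routes joined by 'or' may carry different conditions without contradicting each other. That irregular cycles with a raised FSH leave some chance of conception is general clinical knowledge, not a statement in the protocol. This stands in part: it makes the point a design choice rather than an error. But the protocol's own 12-month rule shows the same caution, and this bullet alone sets it aside.
- **The literal stem closes the gap.** It would, but only by emptying the postmenopause list of effect, so a site is unlikely to apply it that way.
- **The route is narrow.** This stands. FSH is in neither Table 5.1.1 nor the Appendix 2 panels, so the value must already be on record or come from an unscheduled test. Without it, a woman with irregular periods stays WOCBP.
- **Other safeguards exist.** There is medical history at screening and Day 1, a complete physical examination including genitourinary on Day -3 and Day 1, adverse event assessment from Day -3, exclusion 6f, and sections 6.1.1 and 6.4 for any pregnant subject. They reduce the risk, but none is an HCG test.

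A reader might also infer that the HRT bullet opens a second and wider route, since as printed it has no age, amenorrhea or FSH condition. The document does not support that firmly. The bullet follows a note that interrupts the list and may be a fragment of a longer line or a product of the layout. It forms no part of this point.

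**Conclusion.** The point holds for the irregular-periods bullet alone, as a minor and optional safety clarification. A woman who meets that bullet and is unsterilised, not abstinent, using no method and with a non-sterile partner is outside criteria 3b and 3c, the section 3.4.3 duty and all six scheduled urine tests. Because subjects are inpatient until Day 7, the main risk is a pregnancy already present at entry; conception in the outpatient dosing week is the lesser one.

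This rests on the 'and' reading of the stem and on the clinical premise noted above. The figure of 0 to 2 women is an assumption, and the true number may be zero. It would be wrong to infer any effect on the trial's results: no endpoint, analysis set or treatment comparison depends on this definition.

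**What to change.** Delete the irregular-periods bullet from section 3.3.3 as a stand-alone route. These women then remain WOCBP unless they meet the first bullet or the age note, and they follow 3b, 3c, 3.4.3 and the existing urine HCG row of Table 5.1.1. No new visit or procedure is needed.

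The cost is a wording change, six site urine tests per woman reclassified (0 to 12 in total under the assumption above), and a contraception requirement for those women, some of whom may have little real chance of conceiving.

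For the HRT bullet, the sponsor need only confirm the intended wording; no new rule is proposed.

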3.4 Concomitant Treatments

3.4.1 Prohibited and/or Restricted Treatments

3.4.1.1 Prohibited Treatments

Once enrolled, subjects may not receive any of the following for the duration of the study:

- Any injectable anti-diabetic medications other than insulin (including GLP-1 agonists and pramlintide)
- Any oral anti-diabetic medications.
- Acetaminophen-containing medications (contraindicated for the DexCom SEVEN PLUS System so subjects should not use medications that contain acetaminophen while wearing the Dexcom CGM device).
- Any diuretic therapy (e.g. loop diuretics, thiazide diuretics, aldosterone antagonists).
- Treatment with any systemic corticosteroid therapy.
- Administration of phentermine, benzphetamine, diethylpropion, methamphetamine, orlistat, and/or phendimetrazine.

3.4.1.2 Restricted Treatments

The following can be administered provided the dose was stable prior to screening and is maintained stable for the duration of the study:

Herbal/over-the-counter preparations:

- St. John's Wort
- Fenugreek
- Flaxseed
- Chromium
- Ginseng.
- Natural agents marketed for lowering blood sugar such as Antibetic[™], Alphabetic[™], Diabetics[™], DB-7[™], Diabetica[™], Diabetiks[™], Dia-Comp[™],DiaVite[™], GlucoCare[™], GlucoTare[™], GlycoNase[™], SugarMax[™] or Sugar Loss[™].

3.4.2 Allowable Treatments and/or Therapies

Subjects may continue on stable doses (as defined by at least 3 months on therapy prior to Day -3, with at least one month on the same dose, per subject report) of angiotensin converting enzyme inhibitors (ACEI), angiotensin II receptor blockers (ARBs), selective serotonin reuptake inhibitors, serotonin-norepinephrine reuptake inhibitors, norepinephrine-dopamine reuptake inhibitors, HMG-CoA reductase inhibitors, ezetimibe, or fenofibrate.

3.4.3 Other Restrictions and Precautions

- Subjects must comply with their prescribed dosing regimen to preserve study integrity and ensure subject safety.
- Subjects should be cautioned that any new prescription, over-the-counter or herbal/nutritional therapies should be discussed thoroughly with the Investigator prior to initiation as concomitant use could result in alterations to their glycemic control and may place them at risk for significant hypoglycemic episodes.
- Subjects must make every attempt to adhere to the diet and exercise counseling (see Section 5.3.7) and to the protocol visit schedule (see Section 5.1.1).
- Women of child-bearing potential must immediately contact the Investigator if they suspect they might be pregnant and if they have changed or plan to change their birth control method (see Section 6.4).

3.5 Discontinuation of Subjects from Treatment

Subjects MUST discontinue investigational product (and noninvestigational product at the discretion of the investigator) for any of the following reasons:

- Withdrawal of informed consent (subject's decision to withdraw for any reason)
- Any clinical adverse event (AE), laboratory abnormality or intercurrent illness which, in the opinion of the investigator, indicates that continued participation in the study is not in the best interest of the subject
- Pregnancy
- Termination of the study by Bristol-Myers Squibb (BMS)
- Loss of ability to freely provide consent through imprisonment or involuntary incarceration for treatment of either a psychiatric or physical (eg, infectious disease) illness

dapagliflozin	MB102072
BMS-512148	Clinical Protocol

- Protocol-defined major hypoglycemia episode or recurrent non-major hypoglycemia episodes (see Section 3.5.1)
- Sustained elevated S_{Cr} (see Section 3.5.2)
- Sustained elevated liver safety abnormalities (see Section 3.5.3)
- Sustained hyponatremia (see Section 3.5.4).
- Sustained elevated CK (see Section 3.5.5)

All subjects who discontinue should comply with protocol specified follow-up procedures for Day 14/ET visit as outlined in Section 5.1. The only exception to this requirement is when a subject withdraws consent for all study procedures or loses the ability to consent freely (ie, is imprisoned or involuntarily incarcerated for the treatment of either a psychiatric or physical illness).

If a subject was withdrawn before completing the study, the reason for withdrawal must be entered on the appropriate case report form (CRF) page.

3.5.1 Discontinuation Guidelines due to Protocol-Defined Major Hypoglycemia Episode or Recurrent Non-Major Hypoglycemia Episodes

Subjects will be discontinued from study medication if they experience severe and/or frequent hypoglycemia episodes, defined as 1 major episode or recurring non-major episodes in the event where the possibility of down-titration of contributing concomitant medication(s) (other than double-blind study medication), and/or other contributing factors (eg, excessive physical activity) have been evaluated and corrected. NOTE: Dose titration of double-blind study medication is not permitted at any time during the treatment period.

- Major Episodes are defined as symptomatic episodes requiring external (3rd party) assistance due to severe impairment in consciousness or behavior with a capillary or plasma glucose value < 54 mg/dL (< 3 mmol/L) and prompt recovery after glucose or glucagon administration
- Recurring Non-Major Episodes are defined as any recurrent hypoglycemia episodes, as determined by the Investigator, not meeting the definition of Major Episodes.

Section 5.3.1 provides additional guidance on management and reporting of hypoglycemia. It is the Investigator's clinical assessment whether subjects who experience non-recurrent and non-major episodes of hypoglycemia should be discontinued from study medication.

